# 15.1 Assessment of Safety

The assessment of seriousness of safety events should be performed by an appropriately delegated, medically qualified member of the site research team.

A safety event is assessed as serious if it:

- Results in death;
- Is life threatening (i.e. the investigator considers the event places the subject at immediate risk of death from the experience as it occurred (this does not include an adverse experience that, had it occurred in a more severe form, might have cause death));
- Requires hospitalisation or prolongation of existing hospitalisation (hospitalisation is defined as an in-patient admission, regardless of length of stay, even if the hospitalisation is a precautionary measure for continued observation. Hospitalisations for a pre-existing condition, including elective procedures that have not worsened, do not constitute an SSAR);
- Results in persistent or significant disability or incapacity (substantial disruption of one's ability to conduct normal life functions);
- Consists of a congenital anomaly or birth defect (in offspring of subjects, or their partners, taking the IMP regardless of time of diagnosis).

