#### 12.3.4 Overdose

Overdose of apixaban may result in a higher risk of bleeding. In the event of haemorrhagic complications, treatment must be discontinued and the source of bleeding investigated. The initiation of appropriate treatment, e.g. surgical haemostasis, the transfusion of fresh frozen plasma or the administration of a reversal agent for factor Xa inhibitors (andexanet alfa) should be considered. Consultation of a coagulation expert should be considered in case of major bleeding. Haemodialysis decreased apixaban AUC by 14% in subjects with end-stage renal disease (ESRD), when a single dose of apixaban 5 mg was administered orally. Therefore, haemodialysis is unlikely to be an effective means of managing apixaban overdose.

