## 12.4.3.1 Liver effects

Liver function tests should be performed before the initiation of treatment and periodically thereafter. Patients who develop any signs or symptoms suggestive of liver injury should have liver function tests performed. Patients who develop increased transaminase levels should be monitored until the abnormality resolves. Should an increase in transaminases of greater than five times the upper limit of normal (ULN) be recorded, atorvastatin should be withdrawn.

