### 15 SAFETY REPORTING

Safety reporting in clinical trials is a legal and ethical requirement and it is imperative that all applicable requirements detailed here are followed during the trial.

HEAL-COVID will **only** report Serious Adverse Events that are believed with a reasonable probability to be due to one of the study treatments i.e. a Suspected Serious Adverse Reactions (SSAR).

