### 15.9.1 Safety Reports

Safety reports will be generated during the course of the trial which allows for monitoring of SSARs including reporting rates and SSARs by arm. The LCTC will send annual developmental safety update reports (DSURs)/Annual Progress Reports (APRs) containing a list of all SSARs to the IDSMC, MHRA and main REC. If any safety reports identify issues that have implications for the safety of trial participants, the PIs at all institutions participating in the trial will be notified.

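### The seriousness list in 15.1 has no medically important category, so a suspected reaction that triggers the protocol's own withdrawal rule can fall outside SSAR reporting

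*Protocol*

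**What the plan says.** Section 15.1 introduces the seriousness definition with "A safety event is assessed as serious if it" and gives five bullets. The admission bullet reads "Requires hospitalisation or prolongation of existing hospitalisation" and specifies that "hospitalisation is defined as an in-patient admission, regardless of length of stay". The threat-to-life bullet applies where "the investigator considers the event places the subject at immediate risk of death from the experience as it occurred". The other three are death, persistent or significant disability, and congenital anomaly. A medically qualified person makes the assessment, but the list gives that person no general criterion of medical importance.

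Section 15 states that the trial will only "report Serious Adverse Events that are believed with a reasonable probability to be due to one of the study treatments", that is, SSARs. Section 9.3 lists SSARs as a secondary outcome. Section 15.9.1 bases the safety reports on "monitoring of SSARs including reporting rates and SSARs by arm". Section 15.9 expedites to the regulator only events that are serious, related and unexpected.

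Section 12 names reactions that end treatment:

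- Section 12.4.3.1, on atorvastatin: "Should an increase in transaminases of greater than five times the upper limit of normal (ULN) be recorded, atorvastatin should be withdrawn".
- Section 12.3.4, on apixaban and under the heading Overdose: "In the event of haemorrhagic complications, treatment must be discontinued and the source of bleeding investigated".

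**The concern.** Seriousness is the entry condition for every formal safety step: the SSAR form, the secondary outcome, the by-arm tables, the annual SSAR lists and SUSAR expediting. If the definition omits a type of event, nothing later in section 15 recovers it. Section 12 treats certain reactions as important enough to end treatment, while 15.1 can class the same reactions as not serious.

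Two things are at stake. The SSAR outcome could undercount drug-related harm of a kind the protocol itself singles out. And the IDSMC, which under 17.4 may require an arm to be stopped for safety, would not see these reactions in the by-arm SSAR reports. The trial is open label with no follow-up visits, so little other event-level safety information is collected.

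**Working it through.** No arithmetic applies. The check is to take the reactions named in section 12 and put them through the definition in 15.1.

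**Case 1: transaminases above 5 × ULN during atorvastatin, suspected to be related, managed out of hospital.**

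| Criterion in 15.1 | Met by the laboratory finding alone? |
|---|---|
| Death | No |
| Immediate threat to life | No |
| In-patient admission or prolongation | No, if managed out of hospital |
| Persistent or significant disability | No |
| Congenital anomaly | No |

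None of the five is met, so the event is not serious and not an SSAR. Section 12.4.3.1 nonetheless calls for withdrawal. The event would fall inside the active monitoring period of 15.4 (randomisation to 30 days after the last dose), so timing is not what excludes it. The course lasts 12 months and 12.4.3.1 asks for periodic liver tests, so detection outside hospital is plausible.

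**Case 2: a bleed on apixaban that is neither immediately life-threatening nor disabling and is treated without admission.** Again none of the five is met. Whether 12.3.4 requires treatment to stop depends on whether its sentence is read as a general rule or as applying to overdose only. The liver rule has no such ambiguity and is enough to establish the point.

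**Consequences, section by section.**

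1. Section 15: not serious, so not reported as an SSAR.
2. Section 9.3: not counted in the SSAR outcome, the only adverse-reaction item on that list.
3. Section 15.9.1: absent from the by-arm SSAR reports and the annual SSAR lists.
4. Section 15.9: not expedited even if unexpected, because a SUSAR must be serious.

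**Other places where such an event might surface.**

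- Section 13.9 asks for the reasons to be documented when trial activities cannot be completed, but does not make them a safety report.
- FACT-GP5 (9.3.1) is a single item on how far side effects bother the participant. It identifies no event, and 13.2 lets participants decline the questionnaires.
- Linked data (13.8.1, 16.2) cover dispensing, outpatient, emergency and primary care use, but carry no investigator judgement of causality and do not feed the SSAR process.

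These sources give non-specific traces and no event-level record of a suspected reaction.

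**The case against.** The strongest reply is that the narrow scope is deliberate. Section 15 stresses that only suspected serious reactions are reported, 15.7 explains the focus, 8.3 points to repurposed drugs with known safety profiles, and 15.10 calls the study pragmatic. That justifies not collecting every adverse event. It does not explain leaving out suspected reactions for which the protocol itself ends treatment. The protocol also already requires notices outside the seriousness definition: pregnancies (15.5) and deaths whether or not related (15.6).

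A second reply is that the definition is wider than it looks. This stands in part. A reader might infer that every reaction goes unreported whenever the patient is not admitted. The text does not support that: fatal, immediately life-threatening or disabling reactions are serious without admission, and any in-patient stay counts however short. The gap covers only reactions that meet none of the five criteria.

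A reader might also infer that muscle reactions belong with bleeding and liver reactions as events that oblige the drug to be stopped. They do not. Section 12.4.3 describes the risk of myopathy but sets no stop rule for it. The only link is indirect: creatine kinase above 10 × ULN is an exclusion criterion (11.2.2), and newly meeting an exclusion criterion is a listed reason for which a participant may discontinue (13.9.1).

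Finally, it would go too far to say that nothing else is recorded. Section 15 limits what is reported, the case report form and the data management plan are not shown, and the IDSMC reviews accumulating data, initially at least monthly. What stands is that the protocol provides no event-level safety report for these reactions.

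**Conclusion.** The point holds in a limited form. The list in 15.1 is closed and contains no medical-judgement criterion. A suspected reaction that meets the atorvastatin withdrawal threshold, and arguably a haemorrhagic complication under 12.3.4, is an SSAR only if it is also fatal, life-threatening, disabling, a congenital anomaly, or leads to or prolongs an in-patient admission.

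No size can be given. The protocol states no rate for such reactions, the two drugs are given for very different periods (14 days and 12 months), and sites report only what they become aware of (15.8.1). Any count per arm would rest on an unsourced rate.

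The conclusion rests on reading the five bullets as exhaustive, which the wording supports and no other section qualifies. It is a worthwhile and inexpensive improvement to safety monitoring. It does not touch the primary outcome, and it is not a finding that the regulations have been breached, which cannot be settled from this document.

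**What to change.** Add one criterion to 15.1 and to the SSAR form: the event is otherwise judged medically important by the medically qualified assessor. Give a suspected reaction that meets a withdrawal threshold in section 12 as an example to inform that judgement. It should not be serious automatically, or a trivial bleed could qualify.

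Reconcile section 12 with 15.1 in the same amendment, including whether the sentence on haemorrhagic complications in 12.3.4 applies beyond overdose. This changes reporting only and leaves open when or how treatment is stopped.

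The cost is a short amendment, a revised form and some additional SSARs. Under 15.8 and 15.9 each of these needs a telephone call, a form within 24 hours, MedDRA coding, Chief Investigator review and follow-up until recovery or stabilisation. The gain is also limited: 13.8.1 schedules no laboratory tests after baseline and there are no follow-up visits, so only reactions that sites learn of would be captured.

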# 15.2 Assessment of "Causality" - Relationship to Trial Treatment/Intervention

The assignment of the causality should be made using the definitions in the table below:

Table 2: Definitions of Causality

Relationship	Description
Unrelated	There is no evidence of any causal relationship.
Unlikely	There is little evidence to suggest there is a causal relationship (e.g. the event did not occur within a reasonable time after administration of the trial medication). There is another reasonable explanation for the event (e.g. the participant's clinical condition, other concomitant treatment).
Possibly	There is some evidence to suggest a causal relationship (e.g. because the event occurs within a reasonable time after administration of the trial medication). However, the influence of other factors may have contributed to the event (e.g. the participant's clinical condition, other concomitant treatments).
Probably	There is evidence to suggest a causal relationship and the influence of other factors is unlikely.
Almost certainly	There is clear evidence to suggest a causal relationship and other possible contributing factors can be ruled out.

IRAS ID: 294861 Page **39** of **64** 

HEAL-COVID will only report events that are assessed as being possibly, probably or almost certainly related to the trial treatment.

In making this assessment, there should be consideration of the probability of an alternative cause (for example, COVID-19 itself or some other condition preceding randomisation), the timing of the event with respect to study treatment, the response to withdrawal of the study treatment, and (where appropriate) the response to subsequent re-challenge.

If any doubt about the causality exists the local investigator should inform the LCTC who will notify the CI. If causality is not determined by the investigator, the causality is considered as related and then the Sponsor representative will add a second causality assessment. The opinion of the treating investigator will never be downgraded.

# 15.3 Assessment of Expectedness

The Chief Investigator and Lead Investigator for the HEAL-COVID trial are responsible for assessing whether a safety event is expected or unexpected, however the Chief or Lead Investigator will not assess their own patients. There is no requirement for a reporting investigator to assess expectedness.

An event will be considered unexpected if it is not listed within the current and approved reference safety information (RSI) (see section 15.3.1) for the study at the time of the event's onset. The nature, severity, or frequency of the event should be considered—if this is not consistent with that described for the type of event in the RSI the event should be assessed as unexpected.

### 15.3.1 Reference Safety Information / Information used to Assess Expectedness

Section 4.8 of the summary of product characteristics will be used as the Reference Safety Information (RSI) for HEAL-COVID.

# 15.4 Time period for Active Monitoring of Safety Events

Active monitoring of safety events experienced by trial participants will be from the period of randomisation until 30 days from last administration of IMP.

Pregnant women will be followed up until the outcome of the birth (see Section 15.5 for more information on reporting pregnancy).

# 15.5 Reporting of Pregnancy

If pregnancy occurs during either the intervention or follow up period of the trial, this must be notified to the LCTC using the appropriate CRF within 24 hours of the site research team becoming aware. The pregnancy must be followed up by the site research team until outcome and reported to LCTC.

Any pregnancies that result in a safety event assessed as "serious" (e.g. birth defect) must also be reported separately on the appropriate SSAR CRFs. All pregnancies and outcomes reported to LCTC will be notified to the study Sponsor and monitored by trial oversight committees.

All pregnancies and outcomes reported to LCTC will be notified to the study Sponsor and monitored by trial oversight committees.

IRAS ID: 294861 Page **40** of **64** 

# 15.6 Reporting death

If the research team become aware of the death of a participant (whether related to the trial or not) this should be notified to the LCTC using the appropriate CRF.

# 15.7 Notes on safety reporting

The focus of safety reporting will be on those events that, based on a single case, are likely to be related to the study medication. To this end, anticipated events that are either study efficacy endpoints, consequences of the underlying disease, or common in the study population will be exempted from expedited reporting. Thus, the following events will be exempted from expedited reporting:

- (i) Events that are the consequence of COVID-19
- (ii) Common events that are the consequence of conditions present preceding randomisation

Any SSARs that are not exempt will be reviewed by the CI (or delegate) and an assessment made of whether the event is "expected" or not (assessed against the RSI). Any SSARs that are not expected would be considered a Suspected Unexpected Serious Adverse Reaction (SUSAR).

### 15.8 Reporting Procedures

All safety events which are recorded for the study should be reported following the procedures detailed below. The occurrence of a safety event may come to the attention of research staff during routine study visits, from the participant's notes, directly from the participant or by other means.

# 15.8.1 Investigator Reporting Responsibilities

The PI is responsible for ensuring that all SSARs requiring recording during this study, which the local research team become aware of, are reported to LCTC. It is the responsibility of the PI or delegate to assess the seriousness and causality of events. When LCTC receive the SSAR this will be MedDRA coded and provided to the Chief Investigator for agreement along with the RSI to assess causality and expectedness.

Safety events which meet the definition of a SSAR must be reported to the LCTC on an SSAR form and reported immediately and in no circumstances later than 24 hours from becoming aware where they will be appropriately processed.

The SSAR form should be completed by an appropriately delegated member of the research team; the assessments of seriousness and causality must be performed by an appropriately medically qualified person. Minimum reporting information must be provided in initial reports for all studies.

#### 15.8.2 Reporting an initial or follow-up SSAR

The PI or delegate should ensure the actions below are completed for SSARs:

(i) Research sites should telephone the LCTC on [contact] prior to submitting a SSAR report

IRAS ID: 294861 Page **41** of **64** 

- (ii) The SSAR form should be transferred securely within 24 hours to the LCTC Central Safety Team (CST) via email [contact]
- (iii) The responsible investigator must notify their R&D department of the event (as per standard local governance procedures)
- (iv) The participant must be identified by trial number, age or month and year of birth and initials only. The patient's name should not be used on any correspondence
- (v) SSARs must be subsequently followed up in line with the processes below:
  - Follow up must continue until clinical recovery is complete and laboratory results have returned to normal, or until the event has stabilised. N.B. Follow-up may continue after completion of protocol treatment if necessary
  - Follow-up information is noted on a new SSAR form to be transferred securely to the LCTC as soon as more information becomes available
  - Tick the appropriate box on the new SSAR form to identify the type of report; this is dependent on resolution status of the SSAR e.g. follow-up / final

Extra, annotated information and/or copies of pseudonymised test results may be requested from LCTC if required.

# 15.9 LCTC Responsibilities

All SSARs will be forwarded to the Chief Investigator by LCTC within 24 hours of receiving the minimum information from site. The CI (or delegate) will review information provided by site and for all events assessed as "related" will provide an assessment of "expectedness".

Safety events which are assessed as "serious", "related" and "unexpected" will be expedited to the MHRA as a SUSAR within the following timeframes:

- SUSARs which are fatal or life-threatening as soon as possible and in any case no later than 7 days after the LCTC is first aware of the event. If the initial report is incomplete, a complete report will be submitted within an additional 8 days.
- SUSARs that are not fatal or life-threatening within 15 days of the LCTC first becoming aware of the event.

Additionally, SUSARs will be reported to the trial Sponsors and Principal Investigators of participating sites within 14 days.

The LCTC will submit an Annual Safety Report to REC and a Development Safety Update Report to the MHRA on an annual basis.

The PIs at all institutions participating in the trial will be notified of any SUSARs within a reasonable timeline, and if appropriate, accompanied by a summary of the evolving safety profile of the IMP.

IRAS ID: 294861 Page **42** of **64** 

Any concerns raised by the TMG/IDSMC or inconsistencies regarding safety reporting noted at a given site may prompt additional training at sites, with the potential for the LCTC to carry out monitoring visits if there is suspicion of unreported SSAR in patient case notes. Additional training will also be provided if there are unacceptable delays in safety reporting timelines.

### 15.9.1 Safety Reports

Safety reports will be generated during the course of the trial which allows for monitoring of SSARs including reporting rates and SSARs by arm. The LCTC will send annual developmental safety update reports (DSURs)/Annual Progress Reports (APRs) containing a list of all SSARs to the IDSMC, MHRA and main REC. If any safety reports identify issues that have implications for the safety of trial participants, the PIs at all institutions participating in the trial will be notified.

## 15.9.2 Urgent Safety Measures (USMs)

An urgent safety measure (USM) is a procedure to protect clinical trial participants from any immediate hazard to their health and safety but has not previously been defined by the protocol. It can be put in place prior to authorisation by the REC and the MHRA.

The Sponsor/LCTC will notify the MHRA and REC immediately and, in any event, within three days that such a measure has been taken and the reasons why it has been taken. The initial notification to the REC and MHRA will be by telephone (ideally within 24 hours) and a notice in writing will be sent within three days, setting out the reasons for the USM and the plan for further action. After discussion with the REC and MHRA, further action will be agreed, which may include submission of a substantial amendment, a temporary halt, or permanent termination of the trial.

Following notification, if a substantial amendment is required this must be submitted as soon as possible to the REC and ideally within two weeks to the MHRA. If the study is temporarily halted it may not recommence until authorised to do so by the REC/MHRA. If the study is permanently terminated before the date specified for its conclusion (in the original applications to REC and MHRA), the Sponsor should notify the REC and MHRA within 15 days of the date of termination by submitting the formal End of Trial Notification.

#### 15.10 Contact Details and Out-of-hours Medical Cover

As this study is pragmatic of treatments with well-established safety profiles, emergency and out-of-hours medical care will be in line with usual NHS arrangements and local standard practice; no special provision is required for HEAL-COVID participants. All participants will be provided with a copy of the information sheet, which includes information about their participation and contact details for the local research team who may be contacted if necessary. During office hours (9am-5pm), the CI or delegate are able to provide medical advice in relation to participation by contacting the trial manager on [name]

IRAS ID: 294861 Page **43** of **64** 

